Evaluation of Pain Quality in Young Swimmers Suffering from Myofascial Pain Syndrome Using Lidocaine Phonophoresis: A Pilot Study in Physical Therapy Rehabilitation Center in Egypt

Brief description

Myofascial pain syndrome (MPS) is characterized by pain and accompanying muscle spasm, referred pain patterns, stiffness, restricted range of motion caused by trigger points on constricted fibers of the skeletal muscles or fasciae. Myofascial pain syndrome is the most common reason of neck and shoulder pain.

The main goal of MPS treatment is to break down the vicious circle of pain spasm and release of trigger points. Various physical therapy modalities such as trigger point injection, stretching-spray technique, heat packs, and transcutaneous electrical nerve stimulation are used for the treatment of MPS.

Therapeutic ultrasound was developed and widely used in the daily practice of physical therapy and sport medicine for the treatment of a variety of acquired and traumatic conditions in overuse injuries. Phonophoresis is believed to accelerate functional recovery by decreasing pain and promoting healing and it has been used to administer various drugs mainly local anesthetics.

Although many different modalities are available to treat MPS especially therapeutic ultrasound and there was lack of research works that investigated the effect of phonophoresis with local anesthetics on myofascial trigger points, so it was of value to compare between the effect of lidocaine phonophoresis and pulsed ultrasound on MPS in treatment of neck pain in youth swimmers using Pain Quality Assessment Scale as a tool of pain quality evaluation.

Corresponding author

[name]

Email address: [contact]

Data Analysis and Statistical design :

The data will be collected before and after three months of treatment for three groups.

The collected data will be analyzed by two types of statistics as follows:

a) Descriptive statistics: The means and standard deviations.

b) Inferential statistics: By using ANOVA test

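### The plan names only an ANOVA for a before-and-after score, with no dependent variable and no baseline covariate; ANCOVA would generally be more precise

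*Combined protocol and SAP*

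**What the plan says.** Under Brief description, the aim is to "compare between the effect of lidocaine phonophoresis and pulsed ultrasound on MPS" in young swimmers, "using Pain Quality Assessment Scale as a tool of pain quality evaluation". No item, subscale or total of that scale is named as the outcome.

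Under Data Analysis and Statistical design, "The data will be collected before and after three months of treatment for three groups". The analysis list has two entries: "a) Descriptive statistics: The means and standard deviations", and "b) Inferential statistics: By using ANOVA test".

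Nothing else in the document adds a dependent variable, a model, a covariate or a contrast. Allocation, sample size, alpha and power are not stated either. The timing sentence speaks of data in general. That the pain scale is among those data is an inference, but a fair one, since it is the only outcome tool named.

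**The concern.** With three groups and two measurement times, an ANOVA could mean any of three analyses:

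- **Three-month score by group.** The baseline is ignored.
- **Change from baseline by group.** With two times, this is the same test as the group-by-time interaction in a repeated-measures ANOVA.
- **Group main effect of a repeated-measures ANOVA.** This averages the untreated baseline with the three-month score. If it were read as the treatment effect, it would halve the difference.

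The first two are unbiased on average under randomisation. Which of them is more precise depends on the correlation between the pre-treatment and three-month scores, which is not known in advance: with equal SDs, the post score is better below 0.5 and change is better above 0.5. As nothing is fixed, the trial may end up with the weaker analysis, or the choice may be made after the data are seen. Both also carry part of any chance baseline difference into the treatment contrast, and such differences are common in small groups. The baseline score needed to avoid this is already being collected.

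**Working it through.** The document states no sample size, power or effect, so there is no figure of its own to reproduce.

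**Inputs from the document.** Three groups; measurements before treatment and at three months; ANOVA as the only inferential method.

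**Assumptions.** Randomised groups of equal size n; equal SD at both times (set to 1); linear relation with baseline; pre-post correlation ρ of 0.3, 0.5 or 0.7; true difference between two groups of 0.8 SD; two-sided 5%; one pairwise contrast without multiplicity adjustment.

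**Step 1: large-sample variance of a group difference, relative to the post score.** Post score: 1. Change: 2(1 − ρ). ANCOVA: 1 − ρ². Hence ANCOVA/change = (1 − ρ²)/(2(1 − ρ)) = (1 + ρ)/2.

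| ρ | Change | ANCOVA | ANCOVA/change |
|---|---|---|---|
| 0.3 | 1.40 | 0.91 | 0.65 |
| 0.5 | 1.00 | 0.75 | 0.75 |
| 0.7 | 0.60 | 0.51 | 0.85 |

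**Step 2: power, counting the cost of the covariate.** Non-central t with N = 3n and non-centrality 0.8/(SD × √(2/n)). Post score: SD 1. Change: SD √(2(1 − ρ)). Both have N − 3 df. ANCOVA: SD √(1 − ρ²), N − 4 df, and variance multiplied by 1 + 1/(N − 5), which is 1.040, 1.025, 1.018 and 1.012 for n = 10, 15, 20 and 30.

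Power (%), post / change / ANCOVA:

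| n per group | ρ = 0.3 | ρ = 0.5 | ρ = 0.7 |
|---|---|---|---|
| 10 | 41 / 31 / 43 | 41 / 41 / 50 | 41 / 60 / 66 |
| 15 | 57 / 44 / 60 | 57 / 57 / 68 | 57 / 79 / 84 |
| 20 | 70 / 56 / 73 | 70 / 70 / 81 | 70 / 89 / 93 |
| 30 | 86 / 74 / 89 | 86 / 86 / 94 | 86 / 98 / 99 |

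Before rounding, the gain over the better simple analysis runs from 1.2 points (n = 30, ρ = 0.7) to 11.3 (n = 15, ρ = 0.5). Over the worse one it runs from 7.5 (n = 30, ρ = 0.5) to 26.9 (n = 15, ρ = 0.7). Simulation with 40,000 trials per cell agreed: ANCOVA power at n = 20 was 72.9, 81.1 and 93.3%. Type I error was 4.8 to 5.2% for all three methods (n = 10 and 20; ρ = 0.3 and 0.7).

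**Step 3: cost if baseline is uninformative (ρ = 0).** ANCOVA variance rises by about 4% at n = 10 and 2% at n = 20. Power falls from 41 to 39% and from 70 to 69%. ANCOVA overtakes the post score once ρ² exceeds 1 − 1/f, where f is the variance multiplier: ρ of about 0.20 at n = 10, and about 0.30 at n = 5 (f = 1.1).

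**Step 4: chance baseline imbalance.** An observed baseline difference b shifts the post-score contrast by ρb and the change contrast by −(1 − ρ)b. For b = 0.3 SD and ρ = 0.3, 0.5, 0.7, the shifts are 0.09, 0.15, 0.21 SD (post) and 0.21, 0.15, 0.09 SD in the opposite direction (change). The chance that two given groups differ by more than 0.3 SD is 2(1 − Φ(0.3/√(2/n))): 50%, 41%, 34% and 25% for n = 10, 15, 20 and 30.

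**Step 5: overall F test.** Simulated with 3,000 runs, n = 20, true means 0, −0.4 and −0.8 SD:

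| ρ | Post | Change | ANCOVA | Repeated-measures group main effect |
|---|---|---|---|---|
| 0.3 | 0.60 | 0.44 | 0.63 | 0.26 |
| 0.5 | 0.60 | 0.58 | 0.72 | 0.24 |
| 0.7 | 0.59 | 0.83 | 0.88 | 0.21 |

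The main effect does poorly because the difference in the mean of the two scores is (0 + δ)/2 = δ/2.

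**The case against.** The strongest reply is that only the missing dependent variable is a defect visible in the document. Once it is fixed, post-score and change-score ANOVA are valid methods, and preferring ANCOVA is a matter of efficiency. Every precision figure assumes randomisation, which the document never mentions. This is also a pilot with no stated power, alpha or target effect; in very small groups with low correlation, ANCOVA may gain nothing. The 7 to 27 point range is against the worse analysis, which nobody has said would be used.

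Much of this is fair as a limit on the claim. The power figures are illustrations and not properties of this trial. At ρ = 0.3 the gain over the better simple analysis is only about 2 to 3 points. If groups were not randomised, ANCOVA and change-score analysis can target different effects, so the allocation method has to be stated before the model is justified. Naming ANCOVA does not by itself settle which scale score or which contrast comes first.

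It does not overturn the point. The pilot still plans an inferential test, and small groups are where chance imbalance is most likely. The better simple analysis cannot be picked in advance without knowing ρ, whereas ANCOVA is close to or better than both across the range. Moving from a pairwise contrast to the overall F test leaves the ordering unchanged. The main-effect reading is one that the plan does not propose, but it does not exclude it either.

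**Conclusion.** The concern holds and should be fixed. The plan leaves open which of several non-equivalent analyses will be run, and it makes no stated use of the baseline as a covariate. Under randomisation the consequence is lost precision, a treatment contrast that carries chance baseline differences, and room to choose the analysis after seeing the data. It is not bias on average and not an inflated type I error.

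The direction is robust: in large samples ANCOVA is never less precise than either simple analysis, and the small-sample penalty at zero correlation is under 2 power points for 10 or more per group. The size is not known, because n, SD, correlation, alpha and allocation are all absent from the document.

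**What to change.** First, add one sentence stating how swimmers were allocated to the three groups. Then replace the ANOVA entry in Data Analysis and Statistical design with wording such as:

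> ANCOVA with the three-month Pain Quality Assessment Scale score [name the score] as dependent variable, treatment group (three levels) as factor, and the pre-treatment value of the same score as covariate. Baseline-adjusted pairwise group differences will be reported with 95% confidence intervals.

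Say which pairwise difference is primary; the stated aim points to lidocaine phonophoresis against pulsed ultrasound. If allocation was not random, state that adjustment may only partly address baseline differences and that ANCOVA and change-score results may then answer different questions. If a group-by-time ANOVA is also shown, state that the interaction, and not the group main effect, addresses the treatment comparison.

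The cost is wording only, as the baseline is already collected. One degree of freedom is used, and variance rises by about 1% (n = 30 per group) to 4% (n = 10) if baseline and outcome prove uncorrelated.

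### Does timing the second score by three months of treatment bias the lidocaine comparison, through numbing at scoring or loss of early stoppers?

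*Combined protocol and SAP*

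**What the plan says.** The section on data analysis and statistical design gives one sentence on timing: "The data will be collected before and after three months of treatment for three groups". The analysis is means and standard deviations, followed by "Inferential statistics: By using ANOVA test".

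The Brief description gives the aim, to "compare between the effect of lidocaine phonophoresis and pulsed ultrasound on MPS in treatment of neck pain in youth swimmers", and the instrument, "using Pain Quality Assessment Scale as a tool of pain quality evaluation". It places the drug among local anaesthetics when it notes a lack of research on the "effect of phonophoresis with local anesthetics on myofascial trigger points". It also describes the purpose of treating the syndrome in general: "The main goal of MPS treatment is to break down the vicious circle of pain spasm and release of trigger points".

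The document gives no session schedule, visit window, interval between last session and scoring, recall period, sample size or expected dropout. It has no rule for swimmers who stop early. Of the three groups, only lidocaine phonophoresis and pulsed ultrasound are named.

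**The concern.** Two routes to bias seem open.

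- **Numbing at the time of scoring.** If the second score is taken as the last session ends, lidocaine swimmers have just received an anaesthetic and pulsed ultrasound swimmers have not. A short-lived drop in pain would then be counted as three-month benefit, although the Brief description speaks of breaking a pain-spasm cycle and releasing trigger points. Adjusting for baseline would not remove it, because the shift lies in the follow-up score.
- **Early stoppers.** Read strictly, a swimmer who stops at six weeks never completes three months of treatment. If such swimmers are not scored, the ANOVA covers completers only. Where poor response drives stopping, the arm with more stoppers looks better than it is.

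At stake would be a false signal for lidocaine, or a distorted estimate carried into a later trial. Scores not collected at the time cannot be recovered afterwards.

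**Working it through.** The plan has no figure of its own to reproduce. Every numerical input below is an assumption.

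**1. Transient shift, tested with the ANOVA the plan names.** Let lidocaine be shifted by *b* SD and the other two groups by 0, with *n* per group and no lasting effect. The group means are *b*, 0, 0 and their average is *b*/3, so the noncentrality is λ = n[(2b/3)² + 2(b/3)²] = 2nb²/3, with 2 and 3(n − 1) degrees of freedom. At n = 20 and b = 0.3, λ = 2 × 20 × 0.09/3 = 1.2. Rejection rates at a nominal 5%:

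| b (SD) | n = 10 | n = 20 |
|---|---|---|
| 0 | 5% | 5% |
| 0.1 | 5.5% | 6.0% |
| 0.2 | 6.8% | 9.0% |
| 0.3 | 9.3% | 14.5% |
| 0.5 | 17.8% | 33.7% |
| 0.8 | 39.9% | 72.3% |

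These rates assume that every lidocaine swimmer is scored while numb. If only half are, the mean shift halves: a 0.3 SD effect gives b = 0.15 and rates of 6.0% (n = 10) and 7.2% (n = 20).

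**2. Transient shift, lidocaine against ultrasound only.** With n = 20 per group and the pooled error on 3 × 19 = 57 df, the t noncentrality is b√(n/2) = b√10. For b = 0.2, 0.3 and 0.5 this is 0.632, 0.949 and 1.581, and the two-sided rejection rates are 9.5%, 15.4% and 34.3%. With baseline adjustment at correlation 0.5 the residual SD is √(1 − 0.25) = √0.75 = 0.866. The rates become 11.1%, 19.0% and 43.5%, because adjustment sharpens the test without removing the shift.

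**3. Unequal stopping driven by response.** If stoppers would score 0.8 SD worse than completers, leaving them out lowers an arm's mean by its stopping rate × 0.8. With rates of 30% and 10% the contrast moves by 0.30 × 0.8 − 0.10 × 0.8 = 0.16 SD. With equal rates and equal reasons it is 0.

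A second model lets a fraction *d* stop in one arm only, with correlation ρ between stopping and pain. The bias is ρφ(q)/(1 − d), where q is the standard normal quantile at 1 − d. For d = 0.1 and ρ = 0.3 it is 0.3 × 0.1755/0.9 = 0.06 SD. For d = 0.3 and ρ = 0.5 it is 0.5 × 0.3477/0.7 = 0.25 SD. At ρ = 0 it is 0.

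**4. Unequal stopping driven by baseline pain.** Suppose the worst 10% and 30% at baseline stop, and baseline correlates 0.5 with outcome. The unadjusted completer contrast is biased by 0.5 × (0.3477/0.7 − 0.1755/0.9) = 0.5 × (0.497 − 0.195) = 0.15 SD. Baseline adjustment brings this to about 0, so only stopping that depends on response after baseline escapes adjustment.

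**5. What the text requires.** The timing sentence names a period, not a session. A score taken some days after the last session satisfies it, and so does one taken at a set date three months from the first measurement. On that second reading an early stopper also has a scoring date. Nothing in the analysis section restricts the ANOVA to completers.

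**The case for a change.** The strongest case for a change is that the silence is complete. Nothing elsewhere supplies an interval, a recall period or an early-stopper rule, and this is not a redaction, since the statistical section is present in full. Two assessors could follow the sentence in different ways. One of those ways favours lidocaine, and the plan does test between groups, so the pilot label does not make bias harmless. Spelling out the timing would cost little.

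Most of this stands as a description of what is unwritten. It does not show that the plan as written produces bias. Bias through numbing requires scoring close to a session, an effect that lasts until then, and a scale answered for the present moment rather than over a longer recall period. The document settles none of these.

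It also requires that relief under the drug fall outside the effect of interest. The stated aim is to compare the effects of two treatments on pain quality. The sentence on the pain-spasm cycle is background on treating the syndrome, and no off-drug effect is named as the target. If relief under treatment counts, a rejection caused by analgesia is not a false positive.

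Bias through stopping requires stopping that depends on response and differs between arms, together with a decision not to score stoppers. The plan makes no such decision.

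**Conclusion.** No change to the plan follows. The document leaves unwritten when the second score is taken relative to a session and what happens to swimmers who stop early. That is missing detail, not a wrong rule: scoring everyone about three months from baseline, away from a session and in the same way in all three groups, fits the sentence as it stands and would give a sound comparison.

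The possible size runs from nothing upwards. The ANOVA's rejection rate stays at 5% without carry-over and reaches 14.5% for a 0.3 SD shift in every lidocaine swimmer at 20 per group. The stopping bias runs from 0 to about 0.25 SD across the scenarios tried. These figures rest on assumed group sizes, shifts, stopping rates and correlations, so they show what careless conduct could do, not what this plan will do. When the results are reported, it is worth asking when the scores were taken and how many swimmers in each group were not scored.

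### The aim is lidocaine phonophoresis versus pulsed ultrasound, but the plan names only an ANOVA on three undescribed groups and specifies no contrast that answers it

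*Combined protocol and SAP*

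**What the plan says.** The last paragraph of the Brief description gives the purpose: to "compare between the effect of lidocaine phonophoresis and pulsed ultrasound on MPS in treatment of neck pain in youth swimmers". The instrument it names for this is the Pain Quality Assessment Scale. That is one comparison of two treatments on one instrument.

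The section on data analysis and statistical design then states: "The data will be collected before and after three months of treatment for three groups". The groups are not named there, and no third group is described anywhere in the document. Two analysis entries follow: "a) Descriptive statistics: The means and standard deviations" and "b) Inferential statistics: By using ANOVA test".

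The document does not say which ANOVA is meant, which of its effects answers the question, whether contrasts or pairwise tests will follow, how multiplicity is handled, which Pain Quality Assessment Scale score is analysed, or how the baseline measurement enters. The title calls the trial "A Pilot Study in Physical Therapy Rehabilitation Center in Egypt".

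**The concern.** The question concerns one pair of treatments, whereas the F-test of a three-group ANOVA concerns all three means at once. A significant F therefore does not say which groups differ. If lidocaine phonophoresis and pulsed ultrasound do equally well and the third group does better or worse, F may well be significant, and a reader could take that as support for lidocaine. Because the third group is undescribed, nobody can judge from the document how likely this is.

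Two further consequences follow. The plan as written yields neither a test nor an interval for its own question. The open choices (which pair, and whether to analyse the post-treatment score, the change or a baseline-adjusted score) can also be settled after the data have been seen.

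**Working it through.** The plan states no sample size, power, significance level or effect, so there is no figure to reproduce. The structural point needs no numbers; its size is illustrated under assumptions.

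**Structure.** With three groups, the overall F has 2 numerator degrees of freedom and tests μ₁ = μ₂ = μ₃. The stated aim is the single difference μ(lidocaine) − μ(ultrasound), which has 1 degree of freedom. Reading the plan as a repeated-measures ANOVA does not help: with three groups and two time points, the group-by-time F also has (3 − 1)(2 − 1) = 2 numerator degrees of freedom.

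**Assumptions, none from the document.** Equal groups, n = 10, 15, 20 or 30 per group, one continuous score with common SD = 1, two-sided 5%.

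**1. Named treatments equal, third group shifted by d SD.** The noncentrality is λ = n·Σ(μᵢ − μ̄)² = n·(2/3)·d², with 2 and 3n − 3 degrees of freedom. For n = 20 and d = 0.8, λ = 20 × 0.667 × 0.64 = 8.53, the critical F(2, 57) is 3.16, and P(F significant) = 0.723.

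| Third-group shift | n = 10 | n = 15 | n = 20 | n = 30 |
|---|---|---|---|---|
| 0 | 0.05 | 0.05 | 0.05 | 0.05 |
| 0.5 SD | 0.178 | 0.257 | 0.337 | 0.489 |
| 0.8 SD | 0.399 | 0.581 | 0.723 | 0.893 |
| 1.0 SD | 0.581 | 0.785 | 0.900 | 0.982 |

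In simulation at 0.5 and 0.8 SD, the direct contrast of the two named treatments rejects about 5% of the time. Testing that pair only after a significant F rejects 3.6% to 4.9% of the time.

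**2. Baseline adjustment without a contrast.** With an assumed baseline correlation of 0.5, the error variance is multiplied by 1 − 0.5² = 0.75. For n = 10 to 30, F is then significant in 0.224 to 0.616 of trials (0.5 SD) and 0.509 to 0.962 (0.8 SD). Adjustment alone makes the third group's effect on F easier to detect; it does not isolate the pair.

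**3. Power for a true lidocaine–ultrasound difference of 0.8 SD.** The contrast has noncentrality d·√(n/2); at n = 20 this is 0.8 × √10 = 2.53, against a critical t(57) of 2.00. For the overall F, λ = n·d²/2 = 6.4 if the third group lies midway, and 8.53 if it equals ultrasound.

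| Method | n = 10 | n = 15 | n = 20 | n = 30 |
|---|---|---|---|---|
| Contrast, unadjusted | 0.407 | 0.572 | 0.701 | 0.865 |
| Contrast, baseline-adjusted (correlation 0.5) | 0.512 | 0.695 | 0.819 | 0.943 |
| Overall F, third group midway | 0.309 | 0.458 | 0.589 | 0.784 |
| Overall F, third group equal to ultrasound | 0.399 | 0.581 | 0.723 | 0.893 |
| Pair tested only after significant F, midway | 0.286 | 0.438 | 0.572 | 0.775 |
| Pair tested only after significant F, equal to ultrasound | 0.319 | 0.490 | 0.637 | 0.833 |

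The baseline-adjusted probabilities in steps 2 and 3 ignore the small cost of chance baseline imbalance. Simulating the full model lowers most of them by about 1 percentage point (for example 0.81 rather than 0.819 for the contrast at n = 20).

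**4. Precision.** The 95% CI half-width is t·√(2/n) unadjusted and t·√(0.75 × 2/n) adjusted. From n = 10 to n = 30 this runs from 0.92 to 0.51 SD unadjusted and from 0.80 to 0.44 SD adjusted.

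**5. Filling the gap afterwards.** If no group differs, three unadjusted pairwise tests at 5% give a familywise error of 12.3% (simulated, n = 20 per group).

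**The case against.** The plan nowhere says that the overall F is the only or deciding test, and ANOVA is commonly followed by pairwise comparisons. If the pair is tested only after a significant F, its error rate in the scenarios above stays at or below 5%. A significant F caused by the third group is a correct rejection, not a false positive; it misleads only someone who ignores the group means, which the descriptive entry would show if reported by group. All the percentages rest on assumed inputs, and the contrast is not always more powerful: with the third group equal to ultrasound and n = 20, F reaches 72% against 70%. This is also a pilot, where strict confirmatory error control weighs less.

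All of this is fair, and it limits the claim. The figures show what could happen under assumptions; they do not show inflated error in this trial. But a follow-up test that is merely not excluded is not a planned one, and group means and SDs supply no interval for the difference of interest. The pilot label lowers the stakes and makes formal multiplicity control optional; a pilot still needs an estimate for its own question. It is also true that, if the third group were another phonophoresis or ultrasound arm, the contrast might not be unique. That is why naming the groups must come first.

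**Conclusion.** The concern holds and should be fixed. Followed as written, the plan gives no test or interval for the comparison that it sets out to make. This conclusion depends on no assumed number. As an illustration with 10 to 30 per equal group, common SD and a two-sided 5% level, the overall F would be significant in 18% to 98% of trials in which the two named treatments are identical and the third group differs by 0.5 to 1.0 SD. The direct contrast keeps a 5% error rate wherever the third group lies. The case for the contrast rests on answering the stated question and on fixing the analysis in advance; any power gain over F depends on the pattern of means.

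**What to change.** Name the three groups and the Pain Quality Assessment Scale score to be analysed, and confirm that lidocaine minus ultrasound is a single, well-defined contrast. Then replace item b) with text such as:

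> The primary analysis is the planned contrast lidocaine phonophoresis minus pulsed ultrasound in the three-month score, estimated from a three-group model adjusted for the baseline score (ANCOVA, pooled error variance), tested two-sided at 5% and reported with its 95% confidence interval. Comparisons with the third group are secondary. A significant overall F-test alone is not evidence of a lidocaine effect.

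A multiplicity method for the secondary comparisons (for example Holm, or pairwise tests only after a significant overall F) can be added and is optional in a pilot. A contrast within an unadjusted ANOVA would also isolate the pair; baseline adjustment is recommended because it makes use of a measurement already planned and, at a correlation of 0.5, narrows the interval (0.63 to 0.55 SD half-width at n = 20).

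The cost is a few sentences in the analysis section. No patients, visits or measurements are added.

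### Should the two-treatment comparison be kept out of the three-group ANOVA because its standard error would borrow the third group's variance?

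*Combined protocol and SAP*

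**What the plan says.** The Brief description of the combined protocol and SAP gives the aim in these words: "compare between the effect of lidocaine phonophoresis and pulsed ultrasound on MPS in treatment of neck pain in youth swimmers". The outcome instrument named there is the Pain Quality Assessment Scale.

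The section on Data Analysis and Statistical design then says: "The data will be collected before and after three months of treatment for three groups". Two kinds of analysis follow: "a) Descriptive statistics: The means and standard deviations", and "b) Inferential statistics: By using ANOVA test".

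That is the whole analysis plan. It does not give the form of the ANOVA, the response (three-month score, change, or baseline-adjusted score), the contrast, any multiplicity procedure, the alpha level, the group sizes or any SD. The third group is not described. The title calls the work "A Pilot Study in Physical Therapy Rehabilitation Center in Egypt".

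**The concern.** The aim concerns two treatments and the analysis concerns three groups. In a classical one-way ANOVA, the difference between any two groups is judged against a mean square pooled over all three. The confidence interval and p-value for the pair in the aim then depend partly on the spread in a group outside the comparison. If that group is less variable than the other two, the interval is too short and the test rejects too often. If it is more variable, the interval is too long and power is lost.

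A Welch comparison of the two named groups removes this dependence and needs only a sentence of text. At first sight it therefore looks like a free improvement to the study's main comparison.

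**Working it through.** **Inputs.** From the documents: three groups, measurements before and after three months, an unspecified ANOVA, and two named treatments. Everything numerical below is assumed: normal data, two-sided 5% level, SD 1 in each named group, SD *k* in the third group, and group sizes in a range plausible for a pilot. The plan states no figure to reproduce.

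**1. The algebra.**
- Classical ANOVA: SE = √[MSE(1/n₁ + 1/n₂)], where MSE = [(n₁−1)s₁² + (n₂−1)s₂² + (n₃−1)s₃²]/(n₁+n₂+n₃−3). The third variance enters.
- Two-group Welch: SE = √(s₁²/n₁ + s₂²/n₂), with Satterthwaite degrees of freedom. The third variance does not enter.

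So the mechanism is real. With equal group sizes, the ratio of pooled to true SE is about √[(2 + k²)/3]:
- k = 0.76: √(2.578/3) = 0.927
- k = 1: √(3/3) = 1
- k = 1.31: √(3.716/3) = 1.113

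**2. What it does to the error rate** (simulation, 15 per group, nominal 5%).

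| Method for the pair | k = 0.76 | k = 1.31 |
|---|---|---|
| Pooled, unadjusted | 6.8–6.9% | 3.0–3.1% |
| F-gated LSD, all means equal | 3.6% | 1.5% |
| F-gated LSD, third mean far away | 6.9% | 3.0% |
| Tukey | 2.9–3.0% | 1.0% |
| Bonferroni | 2.6% | 0.8% |
| Welch, two groups | 4.9–5.0% | 4.9–5.0% |

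An excess over 5% needs all of the following: a classical ANOVA, a contrast that is unadjusted or gated only by the overall F test, and a smaller variance in the third group (at equal sizes). At k = 0.9 the unadjusted pooled error is 5.8%. On change scores (pre SD 1, correlation 0.5, the same compression after treatment) it is 5.7% if the third group is the compressed one, and 4.3% if both named groups are.

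**3. Where the SD ratios come from.** They are not in the documents. They follow from an assumed 0–10 score with latent SD 2, cut off at the ends of the scale: observed SD 1.49 at mean 1.4 and 1.96 at mean 4.0, so 1.49/1.96 = 0.76. To get k = 0.76, the undescribed third group must also be the one with the lower scores.

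**4. What the alternative costs if the spreads are equal.** The pooled SE is then correct and has more degrees of freedom. At 10 per group these are 3 × 9 = 27 against 2 × 9 = 18, and the critical t is 2.052 against 2.101, so 2.101/2.052 = 1.024. Power for a 0.8 SD difference, pooled against Welch:
- n = 10: 40.9% and 39.1%
- n = 15: 57.1% and 55.9%
- n = 20: 70.0% and 69.2%
- sizes 20/10/15: 52.4% and 49.7%
- n = 5: 21.4% and 18.3%

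At n = 5 with a larger difference, 2.8 × √(2/5) = 1.77 SD, power is 72.9% and 66.4%, and Welch error is about 4.4%.

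**5. The cost against a baseline-adjusted analysis.** The plan collects baseline data, so ANCOVA is a natural form for its ANOVA to take. A two-group ANCOVA also leaves the third group out. With named post-treatment SDs of 0.76 and 1, equal sizes and correlation 0.5, its error is 5.0–5.2% at 10–20 per group. With equal SDs, power for a 0.8 SD difference, Welch (post or change) against ANCOVA:
- n = 10: 39% and 48%, a loss of 9 points
- n = 15: 56% and 67%, a loss of 11 points
- n = 20: 69% and 80%, a loss of 11 points

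**6. The response matters more.** At 15 per group, Welch power on post-treatment and change scores is 56% and 91–92% at correlation 0.8, and 55% and 38% at correlation 0.2. A variance clause that allows either score leaves the larger choice open.

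**The case for a change.** The strongest reply is that the claim is conditional and that each half of it is correct. Nothing in the plan rules out a pooled, unadjusted contrast. A sentence naming the contrast has to be written anyway, and a variance clause could go into it at little cost for 10 or more per group.

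Welch also does more than an ordinary two-group t-test. With named SDs 0.76 and 1, the two-group pooled test has an error of 7.3% at sizes 20/10 and 3.3% at 10/20, against 5.0% for Welch. Group sizes are not given, so imbalance cannot be excluded.

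All of that stands as arithmetic. It makes Welch a defensible choice, but it does not make the plan's choice wrong. Pooling the variance across groups is the ordinary working assumption of ANOVA, and the gain in degrees of freedom is worth most in small groups. The third-group dependence disappears with any two-group analysis, so Welch is not needed for that. Its extra protection matters mainly when sizes and spreads both differ, and the documents show neither.

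**Conclusion.** The concern does not hold. It describes a true property of the classical ANOVA contrast, but the documents neither commit to that contrast nor give a reason to expect unequal spreads.

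Under the assumed ratios, the unadjusted error at 15 per group moves from 5% to about 7% or about 3%. It stays below 5% under Tukey or Bonferroni in the cases examined. Under equal spreads the pooled analysis is valid and a little more powerful. The proposed replacement costs about 1–2 points of power at 10–20 per group, about 3–6 points at 5 per group depending on the difference assumed, and 9–11 points against ANCOVA at correlation 0.5. Experienced statisticians could reasonably choose differently here.

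What remains is a shortage of detail: the plan does not name the contrast, the response or the group sizes. That is a separate and larger matter, and the choice of variance estimate follows from it. All sizes quoted rest on assumed SDs, correlations and group sizes, because the plan states none.
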